Similar to the BPD, we will collect data on a modified SURG-TLX on each of the eligible surgery days. The modified SURG-TLX will be evaluated at the end of each surgery day to assess participant experience throughout the surgery day. The SURG-TLX measures 6 areas: mental demands, physical demands, task complexity, situational stress, and distractions. Each of the 6 areas is rated on a scale of 0 to 100, which is added to generate a sum score. The sum score will then be compared across surgery days with and without the intervention.

Data will also be collected from medical records about each surgery in the study. The following perioperative data will be collected: surgeries performed, operative time, and intraoperative complications (i.e. bladder/bowel injury, large vessel injury, transfusion, allergic reaction, difficulty ventilating, ICU admission).

At the conclusion of the study, an anonymous exit survey will be performed to give all participants an opportunity to provide feedback. Data will be collected on the results of the exit survey. The exit survey will include questions about the participants experience performing the exercises including ease of performing exercises and incorporating into the surgical day.

Randomization

To randomize surgeons, we will first construct Williams squares where exercise follows no exercise (and vice versa) the same number of times.¹⁰ After the Williams squares are constructed and selected, individual sequences are randomly assigned to the surgeon. Sequence randomization will occur according to a predetermined computer-generated scheme prepared by a study statistician.

Statistical Analysis

Descriptive statistics (means, standard deviations, frequencies) will characterize the sample to assess comparability of the intervention and control surgery days. Chi-square test or Fisher's exact test will be used for categorical variables. Continuous variables will be examined for normality using the Shapiro-Wilk test; normally distributed continuous variables will be compared using the Student's t-test and those non-normally distributed will be compared using the Mann-Whitney U test. We will use linear mixed models to test for an association between BPDS and the targeted micro breaks/exercise intervention across surgery days. We will exclude surgeons who do not provide self-reported BPDS data on both days for a certain body part.

Power analysis:

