Surgery days randomized to intraoperative microbreaks and exercises will include standardized breaks lasting approximately 1.5-2 minutes. During these breaks, surgeons will perform a set of targeted stretches or exercises while remaining sterile. These exercises were developed with the assistance of a physician specialized in Physical Medicine and Rehab. The exercises will be performed just before surgical time-out, at a surgically safe and convenient time 45-75 mins after the start of the case and at the end of the case. A surgically safe and convenient time means the surgeon feels that it is safe to take an approximately 1.5-2 minute break during the procedure at that time. Surgeons will skip the microbreak if there is no surgically convenient or safe time during the case. Surgeons will stop the microbreak at any point if needed to ensure patient safety. The microbreaks performed during the surgery may add time to the surgery in approximately 1.5-2 minute increments, however prior studies have shown no difference in operative time with addition of microbreaks. Attached is a document outlining the exercises including photos with exercise cues and a video demonstrating the exercises. Participants will have access to these documents before and during the study.

On each surgery day, participating surgeons will complete the "Surgery Day Questionnaire" which will include the Body Part Discomfort (BPD) scale and Surgery Task Load Index (SURG-TLX). The Corlett and Bishop BPD Scale was originally created in 1976 and is a validated technique to assess work-related discomfort by body part regions.^{11,12}

Another measure of work-related stress during surgery is the SURG-TLX. This is a validated tool based off the NASA-TLX used to assess overall workload including mental demands, physical demands, temporal demands, task complexity, situational stress, and distractions.¹³ At the beginning of all surgery days, the participating surgeon will complete a baseline BPD scale as the first part of the “Surgery Day Questionnaire”. Following each surgery day, the surgeon will complete both the BPD scale and the SURG-TLX survey to complete the “Surgery Day Questionnaire” for that day. Participating surgeons are asked to inform the research team if they develop any new work-related injury during the study period.

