Data will be collected from medical records about each surgery in the study. The following perioperative data will be collected: surgeries performed, operative time, and intraoperative complications.

At the conclusion of the study, an anonymous exit survey will be performed to give all participants an opportunity to provide feedback. Data will be collected on the results of the exit survey.

All data will be collected and stored in our institution’s REDcap, a secure electronic application for research.

Intervention (see PDF document and video attached)

Chest and Shoulder Opener “Elbows in Pockets”

Stand with feet no wider than hip width apart. Extend arms out in front, palms facing forward. Keep the glutes engaged and weight firmly placed through the heels. Take a deep inhale. Then exhale slowly while tilting your head backwards, pulling your elbows towards your glutes as if to place them in your back pockets. As you move, arch your back while pushing up through the sternum to engage your core muscles. As you are doing this, gently guide your elbows down and back, imagining you are placing them “in your pockets”. Allow the head to relax backwards. Hold for 2 seconds, remembering to breathe, and slowly return back to a standing position. Repeat.

Chin Tuck

Look straight ahead. Pull the chin straight backwards towards the back of the neck while inhaling until a gentle stretch is felt in the back of the neck. Exhale as you come forward. The primary motion is pushing the entire head backwards, with only a slight tilt of the chin downwards. It can be help to practice this out of scrub. Doing this, you can place your finger on your and push straight backwards to guide your head in the appropriate motion.

Neck Rotation

Look straight ahead. Turn head to the right, hold for a moment. Return to center. Turn head to the left, hold for a moment. Return to center.

Squat with Truncal rotation (Chair pose with prayer)

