With feet hip width apart, bring palms together in a prayer position. Deeply inhale, then slowly squat down pushing the buttocks back, as if sitting down in a chair while slowly exhaling. Avoid letting the knees in front of the ankles, and go only as low as can be maintained with control. Keep the chest up and slight arch to the back. Then, on an exhale slowly rotate the torso to the left as far as can be comfortably done without moving the hips and continuing to breath. Return to center, then do this motion to the right. Return to center, and rise to a stand.

Forward Bend

Stand straight up, feet hip width apart. Cross arms. Engage the glutes and arch the back. With a slight bend in the knees, inhale and then on your exhale hinge forward at the hips until a stretch is felt in the hamstrings or the low back. Avoid rounding the back and avoid bringing arms close to legs. Stand up slowly keeping the glutes engaged and back straight.

Data Collection Sheet:

Baseline surgeon data:	
Age (years)	
Gender (male/female)	
Weight (lb.)	
Height (in.)	
Dominant hand (right/left)	
Years practicing surgery since residency	
Number of cases performed per year	
Number of hours exercising per week in the past month (hrs)	
Data for each surgery day:	
Surgeon BPDS score at beginning of day	
Surgeon BPDS score at end of day	
Surgeon SURG-TLX score at end of surgery day	
Data for each surgery:	
Hysterectomy performed	

Route of Surgery	
Operative time (surgery start time to surgery stop time)	
Intraoperative complications	
Exit survey:	
The intraoperative exercises helped to reduce discomfort: (strongly disagree/disagree/agree/strongly agree)	
It was easy to understand the exercises as demonstrated in the video: (strongly disagree/disagree/agree/strongly agree)	
It was easy to understand the exercises as demonstrated in the PDF document: (strongly disagree/disagree/agree/strongly agree)	
I had to modify the exercises as demonstrated in the PDF document: (strongly disagree/disagree/agree/strongly agree)	
The intraoperative exercises did NOT disrupt the workflow in the operating room: (strongly disagree/disagree/agree/strongly agree)	
I will perform the intraoperative exercises (or some modification of them) in my future practice (strongly disagree/disagree/agree/strongly agree)	
I developed a work-related musculoskeletal disorder during the course of the study: (No/yes)	

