38 There are anticipated benefits to participants.

39 If applicable, describe the potential direct benefits to participants.

To input text, click in the light grey area below.

Participants may directly benefit from the intervention and may experience decreased work-related pain or discomfort.

RISKS

40 Describe the risks associated with each activity in this research

To input text, click in the light grey area below.

Participants are at risk for musculoskeletal injury from the exercises and stretches that are performed in this study.

Surgeries performed during this study may include a surgical lasting approximately 1.5-2 minutes. This could potentially increase the operative time of procedures, although prior studies have shown that there is no significant difference in operative time with the institution of microbreaks⁷.

41 Describe how each risk is mitigated/minimized.

To input text, click in the light grey area below.

The risk of musculoskeletal injury are mitigated by ensuring that exercises and stretches included in this study are gentle and can be performed with minimal strain and exertion. The exercises were developed with the assistance of a physician specialized in Physical Medicine and Rehab.

To ensure that surgical microbreaks do not interfere with patient safety, microbreaks with exercises will only be performed if it is safe. Surgeons will remain sterile during the microbreak and can respond promptly to any patient concerns during the microbreak. The surgeon can stop or skip microbreaks at any point in the study if it is deemed unsafe.

Data Safety Monitoring

For additional information regarding data safety monitoring boards and data safety monitoring plans, please see Section 21 of our [Policies and Procedures](#).

Click on the check box (or double click and type an "X" if using Google Docs).

42 **In the investigator's opinion, this study is minimal risk and does not require a Data Safety Monitoring Plan (DSMP) or a Data Safety Monitoring Board (DSMB).**

PLEASE NOTE: The IRB may determine minimal risk studies do require data safety monitoring under certain circumstances (e.g., if there is a known risk with an expected frequency).

43 **This study does not have a Data Safety Monitoring Board, but researchers have an internal plan/policy to monitor for safety.**

Complete Data Safety Monitoring Details (44-51).

44 **This study has a Data Safety Monitoring Board (DSMB).**

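### Staying sterile during the exercises is one of the stated patient safeguards, but no form in the plan systematically asks whether sterility was broken

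*Combined protocol and SAP*

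**What the plan says.** **The safeguard.** Section 11 (Procedure Description) states that in each break "surgeons will perform a set of targeted stretches or exercises while remaining sterile". Section 41, on how risks are reduced, repeats this as a protection for patients: "Surgeons will remain sterile during the microbreak and can respond promptly to any patient concerns during the microbreak". It is not the only one. The same section says that "microbreaks with exercises will only be performed if it is safe", and sections 11 and 41 both let the surgeon skip or stop a break.

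**The movements and their timing.** Section 11 describes arms extended forward, elbows drawn down and back, a squat with trunk rotation, and a forward bend with the caution "Avoid rounding the back and avoid bringing arms close to legs". Sets are placed just before time-out, at 45-75 minutes into the case, and at the end of the case. The first two are followed by further operating.

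**What is recorded.** In section 5, under the secondary outcome: "Data will also be collected from medical records about each surgery in the study". The complications are then spelled out, after an i.e., as "bladder/bowel injury, large vessel injury, transfusion, allergic reaction, difficulty ventilating, ICU admission". Section 11 restates the items as "surgeries performed, operative time, and intraoperative complications" and adds nothing. The Data Collection Sheet has four fields per surgery: hysterectomy, route, operative time, and "Intraoperative complications" without further definition. The exit survey covers benefit, clarity of the instructions, modification, workflow, future use and new musculoskeletal disorder, and ends with a free-text comment. No post-operative follow-up of patients is described.

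**What the trial hopes to say.** Section 3 (Study Background) hypothesises less pain for surgeons with no loss of overall surgical performance.

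**The concern.** Section 40 names two risks: musculoskeletal injury to the surgeon and longer operative time. Each has a route into the data. Operative time is abstracted for every surgery, and new work-related injury is to be reported to the team and is asked about at exit. Keeping sterile differs. It is a condition of the intervention and is offered as a patient safeguard, yet nothing routinely shows whether it was kept.

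This affects interpretation. If the listed complications prove similar on exercise and control days, a reader may take that as support for the performance part of the background hypothesis. The comparison would say little about contamination or re-gowning, because neither is on the list and neither is asked about. The gap also cannot be repaired later: a brief contamination handled by a glove change may leave no trace in the medical record.

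**Working it through.** **Document check.** No figure in the plan is at issue, so there is none to reproduce. The places where a break in sterility could be recorded are:

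| Place | Sterility item? | Could it catch an event anyway? |
|---|---|---|
| Section 5, complications list | 0 of 6 | Not if i.e. closes the list; possibly if the six are examples |
| Section 11, Data Collection Sheet, per-surgery fields | 0 of 4 | Possibly, in the undefined complications field, if the medical record mentions it |
| Surgery Day Questionnaire, as described in section 11 | None described (discomfort scale and task load index) | No described route |
| Exit survey | None | Possibly, in the free-text comment, but the survey is anonymous and cannot be tied to a surgery day |

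Capture is therefore incidental.

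**What a direct question could show (illustration).** Inputs:

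- Exercise days: section 14 gives at least 20 surgeons and at least 10 exercise days each, so n = 20 x 10 = 200, and likewise 200 control days.
- Rate of sterility breaks per day: not in the documents. Assumed range 0.5% to 5%.
- Days treated as independent.

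*Upper limit if none is reported:* 1 - 0.05^(1/n) = 1 - 0.05^(1/200) = 0.0149, about 1.5% per exercise day.

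*Chance of at least one event in 200 days:* 1 - (1 - p)^200.

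| Assumed p per day | Expected events, 200p | P(at least one) |
|---|---|---|
| 0.5% | 1 | 0.63 |
| 1% | 2 | 0.87 |
| 2% | 4 | 0.98 |
| 5% | 10 | >0.99 |

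*Sensitivity to independence:* days are clustered within surgeons. At the extreme where all of a surgeon's days behave alike, the effective number is 20, and zero events gives 1 - 0.05^(1/20) = 0.139. The 1.5% limit is thus the favourable end of a range from 1.5% to 13.9%.

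**Comparing day types.** With 200 days per condition and two-sided 0.05, power = Phi[(|p1 - p2| - 1.96 SE0)/SE1], where SE0 = sqrt(2 pbar(1 - pbar)/200) and SE1 = sqrt((p1(1 - p1) + p2(1 - p2))/200). For 1% against 5%: SE0 = 0.01706, SE1 = 0.01694, and (0.04 - 1.96 x 0.01706)/0.01694 = 0.39, so power is 0.65.

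| Control vs exercise (assumed) | Power |
|---|---|
| 0.5% vs 2% | 0.27 |
| 1% vs 3% | 0.30 |
| 1% vs 5% | 0.65 |
| 0.5% vs 5% | 0.79 |

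The normal approximation is rough for such rare events, and clustering is ignored. The item would describe safety; it could not support a formal test.

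**The case against.** A reader might infer more than the documents support, in four ways.

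- **That patient safety depends on sterility alone.** It does not. Section 41 also relies on doing breaks only when safe, on prompt response, and on stopping or skipping. This objection stands in full, although none of those measures records whether sterility was kept.
- **That the trial is blind to sterility breaks, with a recorded count of zero whatever happens.** That would need a closed complications list and no other route. The data sheet's complications field is undefined, and the exit survey takes free text. The supportable statement is that the event is not systematically asked about.
- **That stretching is shown to cause contamination.** The documents give no rate and no evidence of an increase. The caution about arms and legs reads equally well as a precaution built into the exercise, and no reason for it is stated.
- **That the trial claims to demonstrate preserved sterility.** It does not. The formal hypothesis in section 2 concerns surgeon discomfort only, and performance appears only in the background hypothesis.

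The remedy also has limits. A break in sterility is a process event, not patient harm. The surgeon reporting it knows the day's assignment. Infection would still be uncaptured. The exercise document, the video and the questionnaire form itself are not reproduced, so a relevant item there cannot be ruled out. These points reduce the weight of the concern. They do not supply the missing question in the data collection that the plan describes.

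**Conclusion.** The concern holds in a limited form. Staying sterile is one of several stated patient safeguards, and the data collection described does not systematically ask about a break in it. A hazard specific to the intervention could pass unrecorded, and equality on the listed complications would not be evidence about it.

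Its size can only be illustrated. A direct question over 200 exercise days would probably reveal breaks occurring at 1% per day or more (chance at least 0.87), and a clean record would bound the rate near 1.5%. Both figures assume independent days and complete reporting, and clustering by surgeon would weaken both. Breaks may be skipped, so not every assigned exercise day involves every set.

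This is an inexpensive improvement to descriptive safety data. It does not affect the validity of the primary comparison of discomfort.

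**What to change.** Add one yes/no item to the end-of-day part of the Surgery Day Questionnaire, answered for each case on both exercise and control days: *Was there any break in sterility, or any change of gown or gloves for contamination? If yes, did it occur during an exercise set or at another time?*

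Report the counts by assignment beside the intraoperative complications, without a significance test. Restrict any statement that surgical performance was not compromised to what was measured. State whether the six complications are a closed list or examples, and whether post-operative infection is collected.

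The cost is one short question per case on a form already completed each surgery day, with no added procedures, staff or patients. The downside is unblinded self-report, which may under-count and may differ between day types; the report should say so.

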This is a prospective randomized trial to assess the effect of intraoperative microbreaks and exercises on gynecologic surgeon body discomfort. Surgery days among gynecologic surgeons will be randomized to include or not include intraoperative microbreaks with specific exercises. Data on body part discomfort and surgeon task load will be collected on each surgery day.

[figure not shown]
5 Data Analysis

Describe the data analysis plan, including any statistical procedures or power analysis.

To input text, click in the light grey area below.

Design

Describe the design of your study –

Demographic and baseline characteristics

The baseline survey includes information such as surgeon age, gender, weight, height, dominant hand, surgical volume, years practicing surgery, and activity level.

Nordic Musculoskeletal Questionnaire

At the beginning of the study, each participant will complete a baseline questionnaire adapted from the standardized Nordic Musculoskeletal Questionnaire (NMSQ)⁸ and a survey developed by Plerhoples et al.⁹ The NMSQ is a validated questionnaire for the analysis of musculoskeletal symptoms and assesses for history of trouble (ache, pain, discomfort) in body part regions.

Primary outcome

Body Part Discomfort (BPD) scale

On each of the eligible surgery days, we will collect data on body part discomfort and surgical experience using the Body Part Discomfort (BPD) scale. The BPD scale measures body part discomfort using a 10-point scale (1 corresponds with no discomfort and 10 corresponds to maximum body discomfort) for body part regions. Body part regions include neck, shoulders, arms, wrist/hands, upper back, low back, hips/thighs, knees, ankles/feet. Body part discomfort will be summarized by the mean severity of all ratings by the subjects, known as the Body Part Discomfort Severity (BPDS) index. This summary measure will be calculated from all of the individual BPD ratings for each posture in the present study. We will compare self-reported BPDS at the beginning of the surgery day to the end of the surgery day and calculate the change by subtracting the BPDS reported at the end of day minus beginning of day. When appropriate we will control for the total number of minutes spent in surgery during the day.

Secondary Outcome:

Surgery Task Load Index (SURG-TLX)

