Sample size estimations were conducted using G*Power. We utilized the research by Park et al (2017) to estimate the effect of intraoperative microbreaks and exercises on surgeon body discomfort. Park et al (2017) reported differences in body discomfort between surgeons who completed the intraoperative microbreaks/exercises and the control group that ranged from $d=0.00$ to $d=0.48$. Using G*Power, we computed the required sample size to detect a medium effect with the specified parameters: **power=0.85, $\alpha=.05$, $f=0.25$, and measurements = 10**. This yielded a total sample size of at least 20 surgeons, where each surgeon completes 10 surgery days with the intervention and 10 surgery days without the intervention, with a minimal total of 20 surgery days.

Table 1. Power and sample size estimations for a within-subject design

Cohen's f	f=0.1 small	f=0.15	f=0.20	f=0.25 medium	f=0.30	f=0.35	f=0.40 large
total sample size	power						
10	0.12	0.23	0.41	0.62	0.8	0.9	1.0
15	0.16	0.36	0.62	0.85	1.0	1.0	1.0
20	0.21	0.49	0.79	0.95	1.0	1.0	1.0
25	0.27	0.60	0.89	0.99	1.0	1.0	1.0

STUDY ELEMENT IDENTIFICATION

6 Study Elements

Click on the check box (or double click and type an "X" if using Google Docs) each procedure included in your study.

A full description of all study procedures should be provided in the Procedures (Details) section below and/or the applicable supplement form.

 Bio-specimens	 Biometrics	 Registry or Repository
 Focus Group	 Genetic Analysis	 Genomic Data Sharing
 International Research	 Interview/Survey	 MRI
 Protected Health Information	 Observation	 Radioactive Material/PET/Nuc. Med
 Record Review	 Sensors (Externally Placed)	 Sensors (Inserted)
 Video/Audio Recording	 X-Ray/CT	

7 Study Intervention

Click on the check box (or double click and type an "X" if using Google Docs) if you will implement any of the following interventions.

A full description of all study interventions should be provided in the Procedures (Details) section below and/or the applicable supplement form.

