This study will recruit at least 20 surgeons. Each surgeon will complete at least 10 surgery days with the intervention and at least 10 surgery days without the intervention, which will yield at least 20 surgery days.

15 Sample size rationale

To input text, click in the light grey area below.

Using G*Power, we computed the required sample size to detect a medium effect with the specified parameters: **power=0.85, $\alpha=.05$, $f=0.25$** , and measurements = 10. This yielded a total sample size of at least 20 surgeons, where each surgeon completes 10 surgery days with the intervention and 10 surgery days without the intervention, with a minimal total of 20 surgery days.

SCREENING AND RECRUITMENT

16 Identification and Screening

Click on the check box (or double click and type an "X" if using Google Docs) if true.

- This study involves obtaining information or biospecimens for the purpose of screening, recruiting or determining eligibility of prospective subjects prior to informed consent by either:
1. Oral or written communication with the prospective subject or LAR
 2. By accessing records containing identifiable private information or stored identifiable biospecimens.

17 Identification and/or Screening Procedures

Describe the identification and/or screening procedures below.

To input text, click in the light grey area below.

Surgeons (residents, fellows, and attendings performing gynecologic surgery) will be identified from the Department of Women's Health at the University of Texas at Austin

Dell Medical School. Surgery days for each enrolled surgeon will be screened for inclusion. Surgery days containing at least one gynecologic surgery with two hours of total operating time in one day are eligible for inclusion. The eligible surgery days will then be randomized to standard surgery days or surgery days with the intervention (microbreaks with exercises).

18 Recruitment Overview

Click on the check box (or double click and type an "X" if using Google Docs) all recruitment methods utilized for this research.

 E-mail	 Flyer
 In-Person	 Letter
 Social Media	 Research Pool
 Telephone/Text	 Snowball Sampling
 Web-post	 Word of Mouth

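### The only missing-data rule for the primary outcome does not fit a design with at least 10 days per condition and a single nine-region index, and on no reading does it improve on the planned mixed model

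*Combined protocol and SAP*

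**What the plan says.** Section 5, Statistical Analysis, plans the primary comparison as follows: "We will use linear mixed models to test for an association between BPDS and the targeted micro breaks/exercise intervention across surgery days". The next sentence is the exclusion rule: "We will exclude surgeons who do not provide self-reported BPDS data on both days for a certain body part". No other rule for missing days, unrated regions or incomplete sequences appears.

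The surrounding design is this:

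- **Days.** In the power analysis, "each surgeon completes 10 surgery days with the intervention and 10 surgery days without the intervention". Section 14 makes this a minimum: "Each surgeon will complete at least 10 surgery days with the intervention and at least 10 surgery days without the intervention".
- **Outcome.** Section 5, Primary outcome, lists nine regions: "Body part regions include neck, shoulders, arms, wrist/hands, upper back, low back, hips/thighs, knees, ankles/feet". They are combined into one index: "Body part discomfort will be summarized by the mean severity of all ratings by the subjects". The analysed quantity is a within-day difference; the plan will "calculate the change by subtracting the BPDS reported at the end of day minus beginning of day".
- **Withdrawal.** Item 53 requires participants who develop a work-related or sports-related injury to leave the study. It does not say whether data already collected are kept.
- **Recording.** The data collection sheet in section 11 lists one BPDS score at the beginning and one at the end of each day. It does not list region-level ratings.

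**The concern.** Three parts of the sentence do not match the design.

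1. A rule about both days suits a two-day comparison. Here each surgeon contributes at least 20 days.
2. The rule asks for BPDS data for a body part. BPDS as defined has no body-part version, since it is already the mean over regions.
3. The unit removed is the surgeon, after a sequence has been assigned. The mixed model planned in the sentence before it works across surgery days and does not need complete sequences.

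What is at stake depends on how the sentence is read. The text does not fix the reading, so it could be chosen after the data are seen. On the strict reading, a surgeon with one missing day would take all the usable days out with it, and so would a surgeon who had to withdraw for injury. Injury is plausibly related to discomfort, so dropping those surgeons could shift the estimate as well as reduce precision.

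**Working it through.** **Inputs from the documents.** At least 20 surgeons, and 10 + 10 = 20 days per surgeon, so 20 × 20 = 400 surgeon-days if complete. Nine regions.

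**Assumed inputs.** The documents give no missing rate. I use p = 1%, 2% and 5% missing days. Missing days are either independent or clustered by surgeon as a beta-binomial with intraclass correlation 0.2. There is no stated figure for losses to reproduce.

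**Reading 1: at least one day of each kind.** This is the most natural reading, because the same paragraph aims to "assess comparability of the intervention and control surgery days".

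- Expected surgeons kept, independent: 20 × (1 − p^10)². At p = 5% this is 20.00 to two decimals. Clustered, it is 19.995.
- Early leaver: with k rated days from a random order of 10 and 10, the chance of having only one kind is 2 × C(10,k)/C(20,k). This gives 0.47 for k = 2, 0.21 for k = 3 and 0.03 for k = 5. If days run in exercise/no-exercise pairs, it is 0 from k = 2 on. The sequences are not shown, so both orders are assumptions.

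**Reading 2: every day.** A surgeon is kept only if none of the 20 days is missing.

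- Independent: expected kept = 20 × (1 − p)^20.
- Clustered: with a = 4p and b = 4(1 − p), expected kept = 20 × the product over i = 0 to 19 of (b + i)/(4 + i).

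| p | Kept, independent | Lost | Kept, clustered | Lost |
|---|---|---|---|---|
| 1% | 16.4 | 3.6 | 18.5 | 1.5 |
| 2% | 13.4 | 6.6 | 17.2 | 2.8 |
| 5% | 7.2 | 12.8 | 13.6 | 6.4 |

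In days, at p = 2%: using every available day keeps 400 × 0.98 = 392. Reading 2 keeps 20 × 13.35 = 267 if independent, or 20 × 17.17 = 343 if clustered.

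**Reading 3: both times of the same day.** If q is the chance that one form is missing and incomplete days are dropped one by one, 400 × (1 − q)² days remain: 392, 384 and 361 at q = 1%, 2% and 5%. That is close to the rule proposed below, but the sentence excludes surgeons, not days.

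**Reading 4: scope limited to one region.** The surgeon would be left out of that region's comparison only, and the primary index would be untouched. No region-level comparison is written in the plan.

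**Side check on unrated regions.** Suppose eight regions are rated 2 and low back 6 at both times, so the true change is 0. If low back is unrated at the end of the day, BPDS goes from (8 × 2 + 6)/9 = 2.44 to 16/8 = 2.00, a false change of −0.44. Computed from the same eight regions at both times, the change is 2.00 − 2.00 = 0. This is a hypothetical illustration of a separate scoring gap and does not depend on how both days is read.

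**The case against.** The strongest reply is that the harmful reading is the less natural one. On the most natural reading almost nobody is lost, and on the same-day or single-region readings the primary analysis barely changes. That stands: what is certain is the misfit, while the size of the loss is conditional. Section 14 also sets a minimum, so missed days could be replaced, which would reduce every loss under the strict reading except those from withdrawal. And every missing rate used here is assumed.

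A reader might infer that the rule will cost the trial its planned power of 0.85. The documents do not support that. The f = 0.25 column of Table 1 can be reproduced with a test on 9 degrees of freedom over 10 measurements and an assumed correlation of 0.5 (computed 0.63, 0.85, 0.95 and 0.99 for 10, 15, 20 and 25 surgeons; printed 0.62, 0.85, 0.95 and 0.99). But that is not the exercise against no-exercise contrast. With 7 surgeons it gives 0.44, whereas the two-condition contrast, assuming d = 0.5 and correlation 0.5, gives 0.93 to 0.47 as the between-surgeon SD of the effect goes from 0 to 0.5. The answer depends on the test and on inputs the plan does not give, so no power loss should be quoted.

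A mixed model also relies on a missing-at-random assumption. True, but excluding surgeons needs an assumption at least as strong, namely that those kept represent those removed.

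What the reply does not remove is that nothing in the plan selects a reading, and that none of the readings makes the exclusion better than analysing the usable days.

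**Conclusion.** The point holds as a defect in the analysis rule that should be fixed before analysis. The sentence fits neither the number of days nor the definition of the outcome, and no other section repairs it.

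Its effect ranges from almost nothing (at least one day of each kind) to a loss of 3.6, 6.6 or 12.8 of 20 surgeons (every day; 1%, 2% or 5% independent missing days), or 1.5, 2.8 or 6.4 if clustered. It would be smaller with replacement of missed days. These figures rest on assumed rates and an assumed intraclass correlation of 0.2.

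It would be wrong to conclude that the plan will discard many surgeons. The text permits that reading but does not require it. Confidence is high that the rule does not fit, and much lower about how much harm would follow.

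**What to change.** Replace the exclusion sentence with: *All randomised surgeons, and every surgery day with both a beginning-of-day and an end-of-day BPDS, are analysed as assigned in the linear mixed model; no surgeon is excluded for missing days, and data up to withdrawal are retained. Missing days are reported by condition and reason.*

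As a separate scoring note, state before analysis that the BPDS change for a day is computed from the regions rated at both times. This requires keeping the region-level ratings from the Surgery Day Questionnaire in the dataset, because the data collection sheet lists only the BPDS score.

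The cost is one short paragraph and, for the scoring note, the region fields in the database. No new assessment is needed, since the BPD scale is already completed at both times. The remaining downside is the reliance on missing-at-random, which the report by condition and reason lets readers judge.
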